## **Statistical analysis plan**

### **General principles**

Analyses will be intent-to-treat, including all participants randomized at Visit 1, except when noted. We will use a critical alpha of 0.05 or 95% confidence intervals, and two-tailed tests to conduct all statistical tests.

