### **Predictions**

We predict that front-of-package alcohol health warnings will lead to fewer drinks consumed per day (primary outcome), compared to the control. In terms of secondary outcomes, we predict that compared to the control, front-of-package alcohol health warnings will lead to

greater intentions to limit drinking, forgoing a drink, perceived control over drinking, learning something new, knowledge of harms from alcohol in warnings, reminding of harms of alcohol, and perceived likelihood of harms from alcohol. We predict that, compared to the control, front-of-package alcohol health warnings will lead to lower maximum number of drinks consumed in a day, proportion of days drinking during the study, and perceived healthfulness of alcohol.

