### **Statistical methods**

We will descriptively present demographic characteristics separately for each trial arm but will not test for balance, following CONSORT guidelines. Assuming sufficient internal consistency (Cronbach's alpha $\geq$ 0.70), we will average responses to all measures with 3 or more items.

All analyses will be intent-to-treat, except where noted. To examine the impact of trial arm on the primary outcome, we will run a mixed effects linear regression model to account for repeated measures across participants. This model will regress number of drinks consumed per day on indicators for trial day when drinking was reported (within subjects, level 1 variable, fixed effect), whether the trial day when drinking was reported was a weekend versus weekday (within subjects, level 1 variable, fixed effect), and trial arm (between subjects, level 2 variable, fixed effect). Analysis will treat the intercept as random. In "per protocol" sensitivity analyses, we will re-run the primary outcome model among those with high adherence to the labeling protocol.

We will explore whether the impact of trial arm on the primary outcome differs by the following participant characteristics: baseline alcohol use, baseline intentions to limit drinking, gender, age, and education. Using the same modeling approach as for the primary outcome and separate models for each moderator, we will regress number of drinks consumed per day on trial arm, the moderator, and interactions between trial arm and the moderator. We will report the statistical significance of the interaction terms. We will estimate the impact of trial arm on the outcome at each level of the moderator, adjusting for these post-hoc tests using a Bonferroni-Holm correction.

Next, we will examine the impact of trial arm on secondary outcomes. We will use mixed effects linear and logistic models for outcomes with repeated measures. The predictor will be trial arm (between subjects, level 2 variable, fixed effect); analyses will treat the intercept as random. We will use standard logistic and linear models for outcomes measured only once, with trial arm as the only predictor.

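### Three secondary outcomes are analysed without the matching baseline values that the plan already names, which gives up precision but not validity

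*Combined protocol and SAP*

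**What the plan says.** The Statistical methods section sets one rule for all secondary outcomes. For those measured repeatedly, "We will use mixed effects linear and logistic models for outcomes with repeated measures", followed by "The predictor will be trial arm (between subjects, level 2 variable, fixed effect); analyses will treat the intercept as random". For the rest, "We will use standard logistic and linear models for outcomes measured only once, with trial arm as the only predictor". Intentions, if taken from several surveys, falls under the first rule. Maximum drinks, being one value per person, falls under the second. Proportion of days drinking could fall under either, depending on whether it is analysed as a person-level value or as a daily yes/no.

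Earlier in that section, the plan will explore whether the effect on the primary outcome "differs by the following participant characteristics: baseline alcohol use, baseline intentions to limit drinking", and other characteristics. These two baseline variables have no other role in the plan.

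The Predictions section lists, among the secondary outcomes expected to rise, "greater intentions to limit drinking, forgoing a drink", and among those expected to fall, "lower maximum number of drinks consumed in a day, proportion of days drinking during the study". No section describes an adjusted secondary analysis or gives a reason for leaving one out. General principles adds: "Analyses will be intent-to-treat, including all participants randomized at Visit 1, except when noted".

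**The concern.** For intentions, the plan names a baseline value of the same construct and then leaves it out of that outcome's model. For maximum drinks and proportion of days drinking, baseline alcohol use is an obvious predictor: heavier and more frequent drinkers at entry are likely to remain so over about three weeks. If baseline predicts outcome, a linear arm-only model leaves explainable between-person variation in the error term. The interval is then wider than the collected data allow, and a real effect is more likely to be missed. This matters because the plan makes a directional prediction for each of the three outcomes and tests each at .05.

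The point covers three of the ten secondary outcomes in the Predictions section. No matching baseline is documented for the other seven.

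**Working it through.** **Inputs.** From Sample size needs: 720 people in two equal arms, 21 diary days, intraclass correlation (ICC) .60, 15% missing. From General principles: two-sided alpha .05. Not in the documents, so assumed: the baseline-to-outcome correlation r (range .3 to .7, with .1 as a low check) and, for intentions, the ICC (.6) and the number of post-label surveys (3).

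**1. The plan's own power figure.** With a single-day SD of 1, the variance of a participant's diary mean is .60 + .40/(21 × .85) = .60 + .40/17.85 = .6224, an SD of .789. The SE of the arm difference is sqrt(4 × .6224/720) = .0588. Power is Φ(.17/.0588 − 1.96) = 82.4% and Φ(.18/.0588 − 1.96) = 86.5%. These agree with the stated >80% and >85%, so the plan's d is in single-day SD units. This figure concerns the primary outcome and is untouched by the present point.

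**2. Linear model, outcome measured once (SD 1).** Arm-only SE = sqrt(4/720) = .0745. Adjusted SE = sqrt(4 × (1 − r²)/720).

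| Assumed r | SE | Ratio to arm-only | Arm-only sample with the same SE, 720/(1 − r²) |
|---|---|---|---|
| .1 | .0742 | .995 | 727 |
| .3 | .0711 | .954 | 791 |
| .5 | .0645 | .866 | 960 |
| .7 | .0532 | .714 | 1,412 |

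The SE falls by about 5%, 13% and 29% at r = .3, .5 and .7. A 2,000-run simulation gave ratios of .954, .868 and .714. The ratio does not depend on any effect size.

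**3. Linear mixed model, repeated outcome.** With k surveys, the variance is ICC + (1 − ICC)/k − r². For k = 3 and ICC .6 this is .7333 − r². The SE is .0638 unadjusted, .0598 at r = .3 (down 6%) and .0518 at r = .5 (down 19%).

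**4. Missing baselines.** If a fraction m is missing completely at random and mean-imputed over both arms combined, the variance factor is 1 − (1 − m)r². At m = .10 the SE ratios are .959, .880 and .748 for r = .3, .5 and .7, so most of the gain survives and nobody is dropped. A 6,000-run simulation at m = .10, with a true effect of .18, gave mean arm estimates of .179 to .180.

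**5. Coarse baseline.** The plan says "We will estimate the impact of trial arm on the outcome at each level of the moderator", so the moderators may be categorised. A median split multiplies r by sqrt(2/π) = .798, and the SE ratios become .971, .917 and .829.

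**6. Standard logistic model.** Take 50% control risk and a covariate slope of 1 log-odds per SD (assumed). Near the null, the SE of the log-odds ratio is sqrt(4/(720 × .25)) = .149 without the covariate. With it, p(1 − p) averages about .2066 over the covariate, so the SE is sqrt(4/(720 × .2066)) = .164. The SE rises. The effect grows more: a conditional odds ratio of .75 corresponds to a marginal one of .79, so the ratio of effect to SE is .288/.164 = 1.75 adjusted against .236/.149 = 1.58 unadjusted. Power improves, but the interval on the log-odds scale does not narrow and the estimand changes.

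**The case against.** The strongest reply is that nothing here is wrong. A uniform arm-only rule is transparent and prespecified, randomization makes it unbiased, and no power target depends on it because only the primary outcome is powered. That stands, and it rules out a reading that some may infer: that the secondary results would be biased or invalid. The documents give no support for that.

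A reader might also infer that these outcomes are underpowered. Applying d = .18 to a once-measured outcome with SD 1 gives 67.5% unadjusted. But .18 is the primary outcome's effect in single-day SDs, equal to .18/.789 = .228 in SDs of a participant's diary mean. If the primary assumptions are carried over to a diary-averaged outcome, power is 86.5% unadjusted, 89.4% at r = .3 and 94.2% at r = .5. The starting point therefore turns on a choice of units, and the plan states no secondary effect size. No single power figure deserves a headline.

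A third inference is that all three intervals would narrow. Step 6 shows that this fails for a standard logistic model. If daily drinking yes/no is fitted with a random intercept, its odds ratio is already participant-specific and the example in step 6 does not describe it, so no claim about interval width is made there.

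Finally, r is unknown, and the plan does not document the baseline instruments, their scale, or whether the Visit 1 survey precedes labeling. These gaps limit how much can be promised. They do not remove the point, because a weak pre-label covariate costs almost nothing at 720 participants: one residual degree of freedom, an SE factor of about sqrt(718/717) = 1.0007.

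**Conclusion.** The point holds as one about precision only and is best labelled a free improvement. The plan names two baseline variables for moderation of the primary outcome and leaves them out of the three secondary models where they would be expected to help. For a linear model of a once-measured outcome, the SE reduction is about 5%, 13% or 29% at r = .3, .5 or .7. It is negligible at r = .1 and smaller if only a categorised baseline is available. Every r is an assumption; the direction of the gain is firm, the amount is not. The narrower-interval claim applies to linear models. The finding does not extend to the primary model, to the stated power, or to the seven secondary outcomes without a documented matching baseline.

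**What to change.** In the secondary-outcome paragraph of Statistical methods:

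1. Include the intentions score taken before labeling as a covariate in the intentions model, and state that it is not an outcome time point.
2. Include baseline alcohol use, in continuous form where available, as a covariate in the models for maximum drinks and proportion of days drinking.
3. Keep all randomized participants by replacing a missing baseline covariate with its mean over both arms combined.
4. Keep the arm-only models as sensitivity analyses.
5. If a logistic model is used, state whether the reported odds ratio is conditional on the covariate (and on the random intercept, if there is one) or marginal.

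The cost is a few sentences of SAP text and a second fit of three models. Since both baseline variables are already named in the plan, no new visits or participants should be needed, provided that the intentions item is asked before labels go on; the revised text should confirm this. The covariates should be fixed before outcome data are examined, so that their choice cannot be questioned later.

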## **Study protocol**

Participants will be invited to attend 3 in-person visits, spaced ~1 week apart. Participants will be instructed to bring 8 days' worth of unopened alcohol containers to each trial visit. Study staff will randomize participants to 1 of 2 trial arms (front-of-package health warnings or control labels) at the first visit. At each visit, staff will apply labels per participants' assigned arm to the front of all alcohol containers. Participants will take a computer survey at each visit. Participants will take a final survey remotely approximately 1 week after the final in-person visit. Participants will answer two questions by text message each day they are in the study.

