### **Sample size needs**

To estimate sample size needs, we assumed 21 repeated daily diary measures, 2 trial arms of equal size, an intraclass correlation of .60, and 15% missingness for any given daily diary measure. Power analyses used mixed effects linear regression, with 1,000 simulations. A sample size of 720 people would provide >85% power to detect effect sizes of  $d=.18$  or larger and >80% power to detect effect sizes of  $d=.17$  or larger. These effect sizes are conservative estimates as prior studies of non-alcoholic beverages indicate effect sizes of sugary drink health warnings on behavior of  $d=.25^1$  and  $d=.41^2$ .

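### The mixed models for repeated secondary outcomes have no survey-occasion term, so unequal loss by arm combined with a drift shared by both arms would put a small bias into the arm estimate.

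*Combined protocol and SAP*

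**What the plan says.** All of the relevant modelling text is in the Statistical methods section.

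- **Primary outcome.** "This model will regress number of drinks consumed per day on indicators for trial day when drinking was reported", together with a weekend-versus-weekday term, trial arm and a random intercept.
- **Repeated secondary outcomes.** Linear or logistic mixed models: "The predictor will be trial arm (between subjects, level 2 variable, fixed effect); analyses will treat the intercept as random". One predictor is named. The sentence does not refer back to the primary model, although the moderator paragraph just before it does.
- **Secondary outcomes measured once.** Ordinary linear or logistic models with arm alone.

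The Study protocol section describes a survey at each of three visits about a week apart, daily text questions, and a fourth survey: "Participants will take a final survey remotely approximately 1 week after the final in-person visit". The General principles section analyses everyone randomized at Visit 1.

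The documents do not say which secondary outcomes are repeated, whether the Visit 1 survey supplies outcome data, how missing secondary data are handled, or what loss is expected in each arm.

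**The concern.** A random-intercept model with arm as its only fixed effect assumes one mean per arm at every survey. Someone who leaves early contributes early responses only; a completer contributes an average over all surveys. If responses drift with time, these two kinds of participant have different expected means for reasons unrelated to the labels. If one arm loses more people, the arms are averaged over different mixes of survey times, and part of the drift appears as an arm difference.

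This can happen even when leaving is unrelated to the outcome. The protection a likelihood-based mixed model usually offers against ignorable dropout depends on a correct mean model, and here the mean over time is left out.

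Drift is plausible for outcomes such as learning something new or being reminded of harms, which may change with repeated exposure or repeated asking. The documents do not state that it occurs. At stake are the estimates and error rates for whichever secondary outcomes are repeated.

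**Working it through.** **1. The plan's own power figure.** This checks that a random-intercept variance formula matches the plan. Inputs from Sample size needs: "we assumed 21 repeated daily diary measures, 2 trial arms of equal size"; "an intraclass correlation of .60"; "15% missingness for any given daily diary measure". General principles gives two-sided alpha .05.

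- Diary days observed: 21 × .85 = 17.85.
- SD of a participant mean: √(.60 + .40/17.85) = .789.
- SE of the arm difference, 360 per arm: .789 × √(2/360) = .0588.
- Power at d = .18: Φ(.18/.0588 − 1.96) = 86.5%. At d = .17: 82.4%.

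Both agree with the stated figures of more than 85% and more than 80%.

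**2. Inputs for the secondary model.** From the documents: 720 participants, 360 per arm, arm as the only fixed effect, random intercept. Assumed:

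- ICC .60, borrowed from the daily diary
- total SD 1
- three outcome surveys
- no label effect
- a linear drift common to both arms, with total size T from first to last survey
- a proportion p of an arm leaving after the first survey
- more loss in the warning arm

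**3. Formula.** A participant with n surveys has weight 1/(.60 + .40/n): 1.000 for n = 1 and 1/.7333 = 1.364 for n = 3. Relative to the first survey, a leaver's expected mean is 0 and a completer's is T/2. The expected arm mean is

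(T/2) × 1.364(1 − p) / [p + 1.364(1 − p)].

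The fraction multiplying T/2 is .9247 at p = .10, .8451 at p = .20 and .7609 at p = .30.

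- 20% v 10%: (.9247 − .8451)/2 = .040, so 4% of T reaches the arm coefficient.
- 30% v 10%: (.9247 − .7609)/2 = .082, so 8% of T.

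**4. Worked case.** Take T = −.60 (−.30 SD per survey), 20% v 10%. Warning arm: −.30 × .8451 = −.254. Control: −.30 × .9247 = −.277. Difference: +.024. The SE is √[1/(360 × 1.291) + 1/(360 × 1.327)] = .065, where 1.291 and 1.327 are the mean weights per participant. The shift is .37 of an SE, and the two-sided rejection rate is Φ(−1.96 + .37) + Φ(−1.96 − .37), about 6.5%.

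| Loss, warning v control | Total drift (SD) | Bias (SD) | Error rate |
|---|---|---|---|
| Equal (15% v 15%) | any | 0 | 5.0% |
| Any | 0 | 0 | 5.0% |
| 20% v 10% | .2 | .008 | 5.2% |
| 20% v 10% | .6 | .024 | 6.5% |
| 30% v 10% | .2 | .016 | 5.7% |
| 30% v 10% | .6 | .049 | 11.6% |
| 18% v 12% | .6 | .014 | 5.6% |
| 20% v 10%, half leaving after the second survey | .6 | .019 | 6.0% |

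Biases are absolute. The sign depends on the direction of drift and on which arm loses more.

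**5. Simulation.** REML random-intercept fits (4,000 runs, T = −.60) gave +.024 SD and 6.9% at 20% v 10%, and +.047 SD and 11.4% at 30% v 10%. With survey indicators added, the bias was within .002 SD, rejection was 4.6% to 5.4%, and the SE was no larger (.0652 v .0654 at 20% v 10%).

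**6. Sensitivity.** For 20% v 10% and a .5 SD total drift, moving the ICC from .4 to .8 moves the bias from .017 to .023 SD with three surveys. With four surveys at ICC .60 it is .019 SD. Only the linear model was calculated; the logistic models were not.

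**The case against.** The best case against acting is that two conditions must hold together and the documents support neither. No section predicts different loss by arm or a drift in any secondary outcome. The only missingness figure, 15%, is per daily diary measure; it is not survey dropout and is not split by arm. Participation lasts about three weeks. The larger worked cases put all loss at the point of greatest leverage; with later or more even loss the bias shrinks, as the table shows. Some listed outcomes, such as maximum drinks in a day and proportion of days drinking, read naturally as one value per person, where occasion terms do not apply. All of this stands, and it sets the severity. It does not remove the omission: the plan does provide for repeated secondary outcomes and names arm as their only predictor.

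Three stronger readings are tempting and unsupported.

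- **That a shared drift as a whole would be read as a label effect.** Only about 4% of it leaks per 10-point gap in early loss.
- **That the trial's main result is at risk.** The primary model already has day indicators.
- **That omitting day and weekend wastes meaningful precision for outcomes from the daily texts.** Arm is a between-participant factor. With 17.85 days at ICC .60, residual variance is .0224/.6224 = 3.6% of the variance of a participant mean, so removing even a tenth of the residual changes the arm SE by about 0.2%.

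**Conclusion.** The concern holds as a conditional, usually small bias confined to secondary outcomes analysed as repeated measures. Under the assumed inputs the bias runs from .008 SD (error 5.2%) through .024 SD (about 6.5%) to .049 SD (11% to 12%). It becomes material only when the loss gap and the drift are both large. Drift, loss rates, timing of loss, number of surveys and the ICC for these outcomes are all assumptions. The documents give no reason to expect the unfavourable combination, and none to exclude it. Severity is low. The case for changing the plan is that the protection is nearly free and is better specified before loss by arm is known than added afterwards.

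**What to change.** Replace the sentence on predictors in the repeated secondary models with: *Fixed effects will be trial arm and indicators for survey occasion (for outcomes analysed from the daily texts, trial day and weekend, as for the primary outcome), with a random intercept.* Apply it to both the linear and the logistic mixed models. State which secondary outcomes are repeated and at which surveys, and report response by arm and survey.

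The cost is one or two SAP sentences and a few degrees of freedom out of 720 participants, with no new data. The change removes bias from a drift shared by both arms. It does not remove bias from drifts that differ by arm, which is possible because only one arm sees warnings, or from loss that depends on unobserved outcomes. It should not be presented as a gain in precision.

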### **Sample size needs**

To estimate sample size needs, we assumed 21 repeated daily diary measures, 2 trial arms of equal size, an intraclass correlation of .60, and 15% missingness for any given daily diary measure. Power analyses used mixed effects linear regression, with 1,000 simulations. A sample size of 720 people would provide >85% power to detect effect sizes of  $d=.18$  or larger and >80% power to detect effect sizes of  $d=.17$  or larger. These effect sizes are conservative estimates as prior studies of non-alcoholic beverages indicate effect sizes of sugary drink health warnings on behavior of  $d=.25^1$  and  $d=.41^2$ .

